10.5 Diet/ Activity/ Other Considerations

10.5.1 Diet

Subjects should maintain a normal diet unless modifications are required to manage an AE such as diarrhea, nausea or vomiting.

10.5.2 Contraception

Pembrolizumab may have adverse effects on a fetus in utero. Furthermore, it is not known if

Roswell Park Protocol No.: I 35316

pembrolizumab has transient adverse effects on the composition of sperm.

For this trial, male subjects will be considered to be of non-reproductive potential if they have azoospermia (whether due to having had a vasectomy or due to an underlying medical condition).

Female subjects will be considered of non-reproductive potential if they are either:

(1) Post-menopausal (defined as at least 12 months with no menses without an alternative medical cause; in women <45 years of age a high follicle stimulating hormone (FSH) level in the postmenopausal range may be used to confirm a post-menopausal state in women not using hormonal contraception or hormonal replacement therapy. In the absence of 12 months of amenorrhea, a single FSH measurement is insufficient.);

OR,

(2) Have had a hysterectomy and/or bilateral oophorectomy, bilateral salpingectomy or bilateral tubal ligation/occlusion, at least 6 weeks prior to screening;

OR

(3) Has a congenital or acquired condition that prevents childbearing.

Female and male subjects of reproductive potential must agree to avoid becoming pregnant or impregnating a partner, respectively, while receiving study drug and for 120 days after the last dose of study drug by complying with one of the following:

(1) practice abstinence[†] from heterosexual activity;

OR

(2) use (or have their partner use) acceptable contraception during heterosexual activity.

Acceptable methods of contraception are‡:

Single method (one of the following is acceptable):

- Intrauterine device (IUD)
- Vasectomy of a female subject's male partner
- Contraceptive rod implanted into the skin

Combination method (requires use of two of the following):

- Diaphragm with spermicide (cannot be used in conjunction with cervical cap/spermicide)
- Cervical cap with spermicide (nulliparous women only)
- Contraceptive sponge (nulliparous women only)
- Male condom or female condom (cannot be used together)
- Hormonal contraceptive: oral contraceptive pill (estrogen/progestin pill or progestin-only pill), contraceptive skin patch, vaginal contraceptive ring, or subcutaneous contraceptive injection

[†]Abstinence (relative to heterosexual activity) can be used as the sole method of contraception if it is consistently employed as the participant's preferred and usual lifestyle and if considered

Roswell Park Protocol No.: I 35316

acceptable by local regulatory agencies and ERCs/IRBs. Periodic abstinence (e.g., calendar, ovulation, sympto-thermal, post-ovulation methods, etc.) and withdrawal are not acceptable methods of contraception.

†If a contraceptive method listed above is restricted by local regulations/guidelines, then it does not qualify as an acceptable method of contraception for participants participating at sites in this country/region.

Participants should be informed that taking the study medication may involve unknown risks to the fetus (unborn baby) if pregnancy were to occur during the study. In order to participate in the study participants of childbearing potential must adhere to the contraception requirement (described above) from the day of study medication initiation (or 14 days prior to the initiation of study medication for oral contraception) throughout the study period up to 120 days after the last dose of trial therapy. If there is any question that a subject of childbearing potential will not reliably comply with the requirements for contraception, that participant should not be entered into the study.

10.5.3 Use in Pregnancy

If a participant inadvertently becomes pregnant while on treatment with pembrolizumab, the subject will immediately be removed from the study. The site will contact the subject at least monthly and document the participant's status until the pregnancy has been completed or terminated. The outcome of the pregnancy will be reported to Roswell Park Compliance and within 2 working days to Merck if the outcome is a serious adverse experience (e.g., death, abortion, congenital anomaly, or other disabling or life-threatening complication to the mother or newborn).

The study investigator will make every effort to obtain permission to follow the outcome of the pregnancy and report the condition of the fetus or newborn to the Merck. If a male subject impregnates his female partner the study personnel at the site must be informed immediately and the pregnancy reported to Roswell Park Compliance and to Merck and followed as described above and in Section 17.4.

10.6 Duration of Treatment

Participants may remain on study and continue to receive treatment in the absence of disease progression, unacceptable toxicity and withdrawal from study, intercurrent illness that prevents further administration of treatment, participant demonstrates an inability/refusal to comply with oral medication regime, participant withdraws from study or, death; whichever occurs first.

If patients have been on pembrolizumab for over 24 months the PI can decide if the patient can come off pembrolizumab and continue on with sorafenib treatment.

11.0 Procedures Involved

Eligibility of each participant will be established prior to enrollment.

Informed consent MUST be completed prior to receiving any study related procedures.

The schedule of procedures and observations for this study is summarized in Appendix E: Schedule of Procedures.

Roswell Park Protocol No.: I 35316

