10.1 Sorafenib

During the first 4-6 weeks following enrollment (Days -28 to -1 or Days -42 to -1) patient will be on sorafenib alone.

The recommended daily dose of sorafenib is 800mg (2 x 200mg tablets taken twice daily) without food (at least 1 hour before or 2 hours after a meal.) However, the starting dose may be adjusted at the discretion of the treating physician based on clinical assessment of the patient

Roswell Park Protocol No.: I 35316

during screening with a minimum dose of sorafenib at 200mg BID.

All patients should report to clinic for toxicity evaluation 2 weeks after starting sorafenib.

NOTE: Management of suspected adverse drug reactions may require temporary interruption and/or dose reduction of sorafenib therapy. However, the sorafenib lead-in phase should not extend to greater than 6 weeks from the start of sorafenib to the start of pembrolizumab (For example: Patient develops toxicity 2 weeks after starting sorafenib, which requires a dose hold for 1 week, then re-starts sorafenib with a dose reduction. That patient must be stable on the new dose for at least 1 week before starting pembrolizumab. In this case, the sorafenib lead-in phase is 5 weeks which is in the acceptable window of 6 weeks from start of sorafenib to start of pembrolizumab). Patients will continue to take sorafenib (po), BID, during each 3-week cycle.

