10.2 Pembrolizumab

Starting with Cycle 1, treatment with pembrolizumab will be administered on Day 1 of each 3-week treatment cycle, after all procedures and assessments have been completed (as detailed on the Schedule of Procedures: Appendix E).

Pembrolizumab will be administered at a fixed dose of 200 mg, using a 30-minute IV infusion. Sites should make every effort to target infusion timing to be as close to 30 minutes as possible. However, given the variability of infusion pumps from site to site, a window between -5 minutes and + 10 minutes is permitted (i.e., infusion time is 30 minutes -5 min and + 10 min).

The Pharmacy Manual contains specific instructions for the preparation of the pembrolizumab infusion and administration of infusion solution.

Toxicities will be assessed upon completion of the first 6 evaluable patients to see if any higher than anticipated occurrence of sorafenib toxicity is seen due to the addition of pembrolizumab.

Reported adverse events (AEs) and potential risks are described in Section 13. Appropriate dose modifications are described in Table 1 (see **Appendix F**).

Pembrolizumab Dose Modifications

Adverse events (both non-serious and serious) associated with pembrolizumab exposure may represent an immunologic etiology. These adverse events may occur shortly after the first dose or several months after the last dose of treatment. Pembrolizumab must be withheld for drug-related toxicities and severe or life-threatening AEs as per Table 1 (**Appendix F**).

Dosing interruptions are permitted in the case of medical / surgical events or logistical reasons not related to study therapy (e.g., elective surgery, unrelated medical events, patient vacation, and/or holidays). Participants should be placed back on study therapy within 3 weeks of the scheduled interruption. The reason for interruption should be documented in the patient's study record.

Management and dose modifications associated with the above AEs are outlined in **Appendix F**.

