Appendix E Schedule of Procedures

Trial Period	Screening	Sorafenib only	Combination (sorafenib + pembrolizumab) Treatment Cycles ³						End of Study ⁴	Post-Treatment		
			1	2	3	4	5	6 ^{3a}		Safety Follow-Up ⁵	Follow Up ⁶	Long Term Follow-Up ⁷
Phase Ib and Phase II:	Baseline¹	Day -28 to Day -1*										
Clinical Assessments												
Medical History and Pre-existing Conditions	X									X		
Prior and Concomitant Medication Review	X ⁸		X ⁹	X ⁹	X ⁹	X ⁹	X ⁹	X ⁹	X ⁹	X ⁹	X ⁹	
Physical Examination ¹⁰ ; including vital signs, body weight, & height ¹¹	X	X ²	X	X	X	X	X	X	X	X		
Child Pugh A	X											
ECOG Performance Status	X		X	X	X				X	X		
Adverse Events		X ²	X	X	X	X	X	X	X	X	X	
Survival Status			X	X	X	X	X	X		X	X	X
Laboratory Procedures												
Hematology: CBC with Differential ¹²	X	X ²	X	X	X	X	X	X	X	X		
Chemistry: CMP ¹³	X	X ²	X	X	X	X	X	X	X	X		
T3, FT4, and TSH ¹⁴	X						X		X	X		
Viral Titers: Hepatitis B and C ²² ; Hepatitis B Surface Antigen (HBsAg) and/or detectable HBV DNA and, Hepatitis C Antibody (anti-HCV)	X						X		X			

Trial Period	Screening	Sorafenib only	Combination (sorafenib + pembrolizumab) Treatment Cycles ³						End of Study ⁴	Post-Treatment		
			1	2	3	4	5	6 ^{3a}		Safety Follow-Up ⁵	Follow Up ⁶	Long Term Follow-Up ⁷
Phase Ib and Phase II:	Baseline¹	Day -28 to Day -1*	1	2	3	4	5	6 ^{3a}				
Ab), and detectable HCV RNA												
Coagulation ¹⁵	X											
Tumor Marker (AFP) ¹⁶	X			X		X			X			
Serum Pregnancy Test	X											
Imaging												
CT of chest, abdomen, and pelvis ¹⁷	X			X		X			X			
Study Drugs												
Sorafenib, po		X	X	X	X	X	X					
Pembrolizumab, IV			X	X	X	X	X	X				
Tumor Biopsies/Archival Tissue Collection/Correlative Studies Blood												
Archival Tissue Collection ¹⁸	X											
Tumor biopsy	X ¹⁸								X ¹⁹			
Correlative Studies Blood Collection ²⁰	X		X			X			X			
Pharmacokinetic Blood Sampling ²¹			X			X			X			

*The sorafenib lead in phase can extend up to Day-42 to Day-1 to allow stabilized dosing.

- 1 Within 28 days prior to start of sorafenib only study treatment (unless otherwise noted.)
- 2 Toxicity assessment within 2 weeks of starting sorafenib lead-in to include a directed physical exam and vitals.

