- 12 Hematology (CBC with automated differentials): WBC, RBC, HGB, HCT, platelets, MCV, MCH, MCHC, % neutrophils, absolute neutrophils, % monocytes, absolute monocytes, % eosinophils, absolute eosinophils, % basophils, absolute basophils, % lymphocyte, absolute lymphocyte, platelet confirmation (as clinically indicated), differential confirmation (as clinically indicated). Note: Participants experiencing Grade 4 neutropenia should be monitored according to institutional guidelines. As needed at each study visit as determined by the treating physician or Investigator.
- 13 Chemistry (CMP): chloride, CO₂, potassium, sodium, BUN, glucose, calcium, creatinine, total protein, albumin, total bilirubin, alkaline phosphatase, AST, ALT, A/G ratio, BUN/creatinine ratio, osmol (Calc), anion gap.
- 14 Every 12 weeks starting from C1D1.
- 15 PT/INR and aPTT at screening and as clinically indicated.
- 16 AFP at screening and at disease assessment: six weeks after C1D1 (end of Cycle two), 12 weeks after C1D1 (end of Cycle four), every nine weeks thereafter, and at disease progression.
- 17 Imaging at Baseline, at Cycle 2 (\pm 1 week), at Cycle 4 (\pm 1 week), and then every 9 weeks (\pm 1 week).
- 18 Archival tissue collection. If available at baseline. Refer to Section 11.3.1.
- 19 Tumor biopsy: Optional at end of treatment Refer to Section 11.3.2
- 20 Prior to the start of sorafenib, at start of Cycle 1, at start of Cycle 4 and Day 1 of every subsequent 4 cycles (Cycle 8, 12, etc.), and end of study treatment. NOTE: At onset of Cycle 1, confirm that patient will actually start pembrolizumab before collecting samples. Refer to Section 11.2 for collection and processing requirements.
- 21 Pharmacokinetic samples will be collected at the start of combination treatment and processed according to Section 11.1. Patients will be advised to hold morning dose of sorafenib until after PK blood draw but before pembrolizumab.
- 22 Viral titers will be measured at baseline (and as clinically indicated in patients who have elevated baseline titers) and at every 12 weeks starting from C1D1 to assess possible effects on outcome: Hepatitis B Surface Antigen (HBsAg) and/or detectable HBV DNA and, Hepatitis C Antibody (anti-HCV Ab), and detectable HCV RNA.

Appendix F Table 1

Table 1: Dose Modification Guidelines for Non-Hepatic Pembrolizumab-Related Adverse Events

Toxicity	Hold Treatment For Grade	Timing for Restarting Treatment	Treatment Discontinuation

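### The only scheduled pregnancy test is at screening, 28 to 70 days before the first pembrolizumab dose, so an unrecognised pregnancy arising in the sorafenib lead-in would not be detected before first exposure

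*Combined protocol and SAP*

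**What the plan says.** Sections 3.2 (criterion 10) and 3.3 exclude pregnant women. Section 11.0 fixes when eligibility is checked: "Eligibility of each participant will be established prior to enrollment". In Appendix E the row "Serum Pregnancy Test" carries one mark, in the screening column, with no footnote and no later mark. Note 1 to that schedule sets the screening window: "Within 28 days prior to start of sorafenib only study treatment".

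Treatment begins with sorafenib alone. Section 10.1 gives this lead-in 4 to 6 weeks, and the footnote to Appendix E agrees: "The sorafenib lead in phase can extend up to Day-42 to Day-1 to allow stabilized dosing". Pembrolizumab follows at Cycle 1 Day 1. The stated conditions for adding it concern sorafenib: a lead-in of no more than 6 weeks and a settled dose. For a patient whose dose was reduced, Section 10.1 says: "That patient must be stable on the new dose for at least 1 week before starting pembrolizumab". Section 10.2 has pembrolizumab given "after all procedures and assessments have been completed" and points to Appendix E, which marks no pregnancy test at that visit. Note 20 says "At onset of Cycle 1, confirm that patient will actually start pembrolizumab before collecting samples", but this governs blood collection and names no pregnancy criterion.

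Section 10.5.2 warns of possible fetal harm and requires contraception from the first day of study medication until 120 days after the last dose. Section 3.1 (criterion 9) asks a participant who is, or thinks she is, pregnant to tell her physician. Section 10.5.3 removes a participant who becomes pregnant while receiving pembrolizumab. Section 17.4 requires investigators to report pregnancies that participants volunteer to them.

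**The concern.** The pregnancy exclusion exists to keep a fetus from being exposed to study drug. For pembrolizumab, the exposure the protocol specifically warns about begins not at enrollment but 4 to 6 weeks later. A single test before enrollment therefore shows the participant's status at the wrong end of the lead-in. If a pregnancy begins in that interval and she does not recognise it, nothing scheduled would reveal it before the infusion. What is at stake is avoidable fetal exposure, not the validity of the efficacy result.

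**Working it through.** The plan states no figure for the age of the test at first pembrolizumab, so there is none to reproduce. It follows from two inputs.

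- W, days from the screening test to the first sorafenib dose: 0 to 28 (Appendix E, note 1). The value 0 assumes the test is done on the day sorafenib starts.
- L, days from the first sorafenib dose to the first pembrolizumab dose: 28 to 42 (Section 10.1 and the Appendix E footnote).

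Age of the test at first pembrolizumab = W + L.

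- Shortest: 0 + 28 = 28 days.
- Longest with a 4-week lead-in: 28 + 28 = 56 days.
- Longest with a 6-week lead-in: 28 + 42 = 70 days.

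The 3-day dosing window in note 3 is not applied here; Section 10.1 separately limits the lead-in to 6 weeks. Because the lead-in alone contributes at least 28 days, narrowing the screening window would not close the gap. Only a test at the end of the lead-in does.

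The next question is whether any other provision would detect a pregnancy in that interval.

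- **Contraception (Sections 3.1 and 10.5.2):** lowers the chance of pregnancy but does not detect one.
- **Telling the physician (Section 3.1):** works only if the participant knows or suspects.
- **Two-week lead-in visit and Cycle 1 Day 1 visit (Appendix E):** examination, adverse events, blood count and chemistry are marked at both. A pregnancy test is marked at neither.
- **Reporting (Section 17.4):** runs from the start of study treatment. Note 1 of Appendix E describes the lead-in as study treatment, so a lead-in pregnancy is reportable, but only once it has been volunteered.
- **Removal (Section 10.5.3):** worded for pregnancy on pembrolizumab. The list of reasons for ending treatment in Section 10.6 does not name pregnancy.

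None of these yields a test result between screening and the first infusion.

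On the primary analysis, Section 9.1 replaces patients removed before the combination starts. A woman withdrawn on a positive Cycle 1 Day 1 test would be replaced, and the rule of 4 or more responders among 27 evaluable patients would stand unchanged.

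**The case against.** The strongest reply is that the protocol already guards against this in several ways. Contraception must be agreed before entry, Section 10.5.2 lists acceptable methods, and a woman whose compliance is in doubt should not be entered. A known pregnancy conflicts with the exclusions, and Section 12.1 lets the investigator stop treatment in the participant's interest. Reporting and follow-up reach back into the lead-in. All of that is correct, and it narrows the gap to an unrecognised pregnancy in a woman under a contraception requirement. It does not close it, because each of these measures either lowers the probability of pregnancy or acts only once the pregnancy is known.

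A reader might also infer a liver problem from the same schedule, since coagulation and the Child-Pugh assessment are likewise marked only at screening: that Child-Pugh class cannot be established when pembrolizumab starts. The documents do not support that. No Child-Pugh score is required at that point. Note 15 provides for "PT/INR and aPTT at screening and as clinically indicated", so INR is not confined to screening. Examination and chemistry, including bilirubin and albumin, are scheduled both in the lead-in and at Cycle 1. Appendix J requires INR in the work-up of a hepatic event of clinical interest. Its Child-Pugh stopping limits (a score of 9 or more, or class C) are absolute, not changes from a Cycle 1 value. No decision in the plan turns on a Cycle 1 Day 1 INR, so adding one is not part of this point.

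**Conclusion.** The point holds for the pregnancy test alone. As written, the plan allows a first pembrolizumab dose on a negative test that is 28 to 70 days old, with no scheduled means of detecting a pregnancy that began in the lead-in. It also gives no removal instruction worded for that case. This rests on reading the single screening mark in Appendix E as the complete testing schedule, with no footnote or other section adding a repeat.

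The number of women affected cannot be estimated: the documents give neither the number of participants of child-bearing potential nor a pregnancy rate under the required contraception. It would be wrong to infer that pregnancy is unguarded in this trial, or that the response-rate result is at risk. This is a narrow safety gap that should be closed because closing it is cheap.

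**What to change.** - In Appendix E, add a pregnancy test at Cycle 1 Day 1 for women of child-bearing potential, with the result reviewed before the infusion. Section 10.2 already places the infusion after that day's procedures, so the added mark makes the test a pre-dose check; a short footnote should say so.
- State the action on a positive result: do not give pembrolizumab, remove the participant from study treatment, and report and follow the pregnancy under Sections 10.5.3 and 17.4.
- Extend the removal rule in Section 10.5.3 to pregnancy arising in the sorafenib lead-in.

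The cost is one routine test with a same-day result, at a visit where blood is already drawn, plus a few words of protocol text. No extra visit is needed, and the sample size and decision rule do not change.

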11.1 Pharmacokinetic Blood Sample Collection and Processing

Blood samples for Pharmacokinetic analysis (plasma) of sorafenib levels will be collected via venipuncture using 1, 10 mL green-top tube.

*Note: Patients to be advised to hold morning dose of sorafenib until after PK blood draw.

The time of two doses of Sorafenib prior to the draw will need to be entered on the specimen requisition form for PK analysis, e.g., Cycle 3 Day 21, enter the time. Sorafenib was taken in the am and pm prior to the Cycle 4 Day 1 PK draw.

Pharmacokinetic sample collection will be obtained on:

- Cycle 1-Day 1 (for sorafenib steady state PK), prior to sorafenib and IV pembrolizumab
- Cycle 4-Day 1 prior to sorafenib and IV pembrolizumab and Day 1 of every subsequent 4 cycles (prior to sorafenib and IV pembrolizumab) until end of study
- End of study treatment

The whole blood samples should be maintained on ice and sent to the Hematological Procurement Facility for processing for plasma: Centrifuge whole blood as soon as possible, or within 30 minutes, at 4°C using a refrigerated centrifuge at approximately 3000 rpm for 10 minutes.

Plasma will be aliquoted into (2) cryovials per time-point. The screw cap polypropylene cryogenic tube will be labeled with the participant's clinical study number and patient study ID, protocol time point, dose, and protocol day and time. The label for each participant's sample will be supplied by each site. The samples will immediately be frozen at -80°C or below. At the completion of the study, all samples will be shipped on dry ice to the BMPK core facility at Roswell Park for analysis:

Roswell Park Cancer Institute
Bioanalytics, Metabolomics & Pharmacokinetics (BMPK) Core Facility
Center for Genetics and Pharmacology, Room L1-140
Refer to Study Number – I 35316
[name]
[name]
[contact]

For additional information regarding the handling of pharmacokinetic samples please contact RPCI's Bioanalytics, Metabolomics & Pharmacokinetics Core Facility laboratory at [contact] (Tel) or [contact] (Fax). Or email [contact] and [contact].

EXTERNAL (NETWORK) SITES: Follow directions above for sample collection and processing. The cryogenic tubes will be labeled with the Subject ID # (unique to Network patients), the clinical study number, protocol time point, dose, and protocol day and time. The samples will immediately be frozen at -80°C or below. Samples are to be stored and batch shipped to the RPCI BMPK Core Facility, on dry ice, at the completion of the study.

Note: Samples cannot be frozen in glass tubes – cryogenic vials must be used.

Frozen samples will be shipped via Fed Express Overnight on dry ice with delivery on Mon-Fri.

Roswell Park Protocol No.: I 35316

NO SATURDAY DELIVERY. Do not ship on a Friday or the day before a holiday.

Note: All investigator or analyzing research laboratories housing research samples need to maintain current Temperature Logs and study-specific Sample Tracking and Shipping Logs. The Principal Investigator/Laboratory Manager must ensure that the stated lab(s) have a process in place to document the receipt/processing/storage/shipping of study-related samples/specimens. This is required for both observational and interventional clinical studies collecting clinical samples.

